7.1 Inclusion Criteria

Subjects must meet ALL of the following inclusion criteria to be enrolled in the study:

1. Age \geq 18 years
2. For women of child-bearing potential, a negative pregnancy test within seven (7) days prior to the index procedure
3. Symptomatic leg ischemia or ischemic ulcerations that do NOT exceed digits of the foot (Rutherford/Becker Classification category 2, 3, 4 or 5)
4. Palpable radial artery with diameter \geq 2.5 mm, as assessed by duplex ultrasound
5. Eligibility for standard surgical repair, if necessary
6. A patient who requires a coronary intervention should have it performed at least seven (7) days prior to treatment of the target lesion
7. The patient must provide documented informed consent and any other documented authorization, as required, prior to initiation of the study procedure
8. Per Investigator assessment, the patient is willing and able to be followed up to 30 days post-procedure for evaluation and complete all required assessments per the study protocol.

Inclusion criteria 9 and 10 AND 11a through 14a OR 11b through 16b (whichever is applicable) would be assessed via baseline angiography performed at the time of index procedure:

9. The Investigator has assessed that the patient is a suitable candidate (i.e. meets all inclusion criteria and none of the exclusion criteria), for treatment of a lesion in the iliac, superficial femoral and/or proximal popliteal arteries via transradial approach and is eligible for conversion from a transradial to transfemoral approach, if it becomes necessary.
10. The guidewire is across the target lesion(s) and located intraluminally within the distal vessel following a transradial approach

Patients whose target lesion is in the iliac artery must meet these additional criteria prior to enrollment:

- 11a. A single *de novo* or restenotic lesion \geq 50% stenosis in the common and/or external iliac artery
- 12a. Stenotic lesion (one long or multiple serial/tandem lesions) \leq 100 mm, by visual assessment, within or across the common or external iliac arteries. The stenosis must be treatable with no more than two stents (while minimizing stent overlap)
- 13a. Reference vessel diameter (RVD) ranging from 4.0 to 9.0 mm by visual assessment

RADIANT / P21-7701

Version: 7.0 / March 21, 2023

Cordis®

14a. Angiographic evidence of a patent profunda or superficial femoral artery in the diseased (target) limb

Patients whose target lesion is in the SFA and/or PPA must meet these additional criteria prior to enrollment:

- 11b. A single *de novo* or restenotic lesion \geq 50% stenosis in the SFA and/or PPA
- 12b. Stenotic lesion (one long or multiple serial/tandem lesions) \leq 150 mm, by visual assessment, within or across the SFA and/or PPA. The stenosis must be treatable with no more than two stents (while minimizing stent overlap)
- 13b. RVD ranging from 4.0 to 7.0 mm by visual assessment
- 14b. All lesions are to be located at least three centimeters proximal to the superior edge of the patella
- 15b. Patent infrapopliteal artery, i.e., single vessel runoff or better with patency (<50% stenosis) of at least one of three vessels to the ankle or foot
- 16b. Adequate aortoiliac or common femoral "inflow" (defined as < 30% stenosis after PTA or stenting) prior to treatment of the target lesion
(defined as < 30% stenosis after PTA or stenting) prior to treatment of the target lesion

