8.1.2 Primary Efficacy Endpoint

Technical success at the conclusion of the index procedure, defined as successful insertion of the S.M.A.R.T. RADIANT™ Vascular Stent System into the peripheral vasculature through the radial artery, successful deployment of the study device (S.M.A.R.T.™ stent) at the intended location, and successful withdrawal of the delivery system without conversion from radial to femoral artery access.

RADIANT / P21-7701

Version: 7.0 / March 21, 2023

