8.4 Rationale for Study Endpoints

Each of the primary and secondary safety and/or efficacy endpoints above aligns with the primary objective of the study in evaluating acute safety and efficacy of the S.M.A.R.T. RADIANT™ Vascular Stent System,

RADIANT / P21-7701

Version: 7.0 / March 21, 2023

when used with the BRITE TIP RADIANT™ Guiding Sheath and SABERX RADIANT™ PTA Balloon Catheter in treating femoropoliteal or iliac artery lesions via a radial artery approach.

Regarding the S.M.A.R.T. RADIANT device in particular: since the investigational S.M.A.R.T. RADIANT delivery system incorporates the CE marked S.M.A.R.T. stent, for which there is an abundance of short-term and long-term clinical data available from its evaluation in previous, Cordis-sponsored studies, the main purpose of this study is to assess the safety and performance (outcomes) of the delivery system versus the stent. There is proven, long-term primary patency through 10 years and low stent fracture rate through 3 years following implantation of the S.M.A.R.T. stent. Therefore, rates of vessel patency, restenosis, stent fractures, etc. have not been included as pre-specified endpoints for this study.

The various health economic endpoints will be used to determine if there are cost savings/benefits, such as decreased procedural/treatment and hospitalization costs, for patients who are eligible for and undergo procedures that can be completed via a transradial versus transfemoral arterial approach. General and disease-specific outcomes assessed via the SF-36 and EQ-5D standarized, validated questionnaires will help determine if there is overall, improved quality-of-life in the short-term in patients that undergo stenting procedures via transradial approach to 30 days post-procedure.

9 Informed Consent

Prior to enrollment and performance of any study-specific activities or procedures, the study team shall:

1. Provide each prospective subject with a full explanation of the study (including all potential benefits and risks) that is also documented (i.e., informed consent form) and ensure they have understood all information that has been presented to them.
 - a. The informed consent form (ICF) should enable the subject to understand:
 - i. the nature, objectives, benefits, implications, risks and inconveniences of the clinical investigation;

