10.2.2 Screen Failures & Pre-Screen Failures

Pre-screen Failures: Pre-screen failures are defined as patients who are confirmed to not qualify for study participation according to the eligibility criteria after review of their medical records (i.e., prior to providing informed consent). Such subjects will neither be treated with the study devices nor followed per protocol.

RADIANT / P21-7701

Version: 7.0 / March 21, 2023

Screen Failures: Any consented patient who is confirmed to not qualify for study participation according to the eligibility criteria will be considered a screen failure and will neither be treated with the study devices nor followed per protocol.

Signed informed consent forms and all applicable documentation including source records indicating rationale for screen failure classification and Screening/Enrollment logs or equivalent forms/screens in the Electronic Data Capture (EDC) system will be reviewed during monitoring visits for all screen failure patients.

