10.3 Enrollment

The subject will be considered enrolled into the study after ALL of the following criteria have been met:

- ICF has been signed/dated by all parties
- All pre-screening and screening assessments have been completed
- Vascular access has been obtained in the radial artery (i.e., time of puncture)
- Subject has been assessed by the site against all study eligibility criteria, including those determined by angiography

11 Treatment Plan

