A formal review of risks will be performed upon completion of this clinical study and incorporated into the risk analysis and clinical evaluation and an update of the benefit-risk conclusions made in both documents.

Additionally, the sponsor and/or designee, including but not limited to the clinical project manager, medical monitor and representatives from its post-market surveillance (complaint handling) groups will review information on individual, site-reported adverse events, device deficiencies and complaints and/or periodic listings of such events to assess for any trends, identify any new risks, etc. that may impact the safety of study subjects.

14 Statistics/Data Analyses

Previous clinical studies of therapeutic Iliac and femoropopliteal artery lesion stent treatments have focused on demonstrating the efficacy and safety of the stents under study. As such, the endpoints centered on how well the stent improved luminal diameter and any major adverse events associated with the stent treatment. There was little if any data captured on the stent delivery systems, or the access artery used in these studies.

The primary objective of the RADIANT study is to evaluate acute safety and efficacy of the S.M.A.R.T. RADIANT™ Vascular Stent System, when used with the BRITE TIP RADIANT™ Guiding Sheath and SABERX RADIANT™ PTA Balloon Catheter, in treating patients with obstructive iliac or femoropopliteal arterial disease via radial artery access. In other words, the focus of this study is on demonstrating the efficacy and safety of the RADIANT delivery system when using radial artery access (as opposed to femoral artery) to deliver the S.M.A.R.T. stent to iliac and femoropopliteal artery lesions (previously approved indications for this stent). Therefore, the efficacy and safety endpoints for this study focus on access and delivery success and any adverse events associated with access and delivery. The aim of this study is to demonstrate the safety and effectiveness with which the new delivery system can access the radial artery to deliver the S.M.A.R.T. stent to obstructive iliac or femoropopliteal lesions.

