14.1 Analysis Population

Analyses for the endpoints will be performed using the intent-to-treat (ITT) population. The ITT population will consist of all subjects enrolled in the study and for whom a device insertion was attempted, regardless of the treatment actually received.

RADIANT / P21-7701

Version: 7.0 / March 21, 2023

The per-protocol analysis population is defined as a sub-group of the ITT population consisting of subjects without protocol deviations that could possibly affect the primary endpoints. Primary endpoint analysis using this population is supportive in nature.

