**6 ANALYSIS POPULATION**

Analyses for the endpoints will be performed using the intent-to-treat (ITT) population. The ITT population will consist of all subjects enrolled in the study, excluding roll-ins, and for whom a device insertion was attempted, regardless of the treatment actually received.

The per-protocol analysis population is defined as a sub-group of the ITT population consisting of subjects without protocol deviations that could possibly affect the primary endpoints. Primary endpoint analysis using this population is supportive in nature.

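### Both primary endpoints are conditional on radial access, transradial wire crossing and an attempted device insertion; the plan should say so and record events from puncture in patients who fail at those steps

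*Protocol*

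**What the plan says.** Entry. Criterion 10 in Protocol 7.1 requires that "The guidewire is across the target lesion(s) and located intraluminally within the distal vessel following a transradial approach". Among the conditions in Protocol 10.3 is "Vascular access has been obtained in the radial artery (i.e., time of puncture"). Sections 11.1 and 13.1 add that a subject counts as enrolled only once angiography has confirmed that the patient qualifies.

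Patients who do not qualify. Under Protocol 10.2.2, a consented patient who fails the criteria "will be considered a screen failure and will neither be treated with the study devices nor followed per protocol". Section 11.4 has the site tell the sponsor, after the index procedure, whether the patient was enrolled or was a screen failure. Screen failures after puncture are therefore foreseen.

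Analysis set. Protocol 14.1 defines ITT as "all subjects enrolled in the study and for whom a device insertion was attempted, regardless of the treatment actually received". SAP section 6 removes roll-ins and otherwise keeps enrolled subjects "for whom a device insertion was attempted, regardless of the treatment actually received".

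Purpose. The opening of Protocol section 14 says that "the efficacy and safety endpoints for this study focus on access and delivery success and any adverse events associated with access and delivery". Section 8.1.2 scores insertion of the stent system "into the peripheral vasculature through the radial artery", then deployment, then withdrawal without femoral conversion. Section 8.4 says that "the main purpose of this study is to assess the safety and performance (outcomes) of the delivery system versus the stent".

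Event capture. Sections 11.1, 13.1 and 13.6 ask for adverse events back to puncture, and for device deficiencies back to first use or handling, in each case for enrolled subjects.

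**The concern.** The failure modes specific to this route that Protocol 5.4.2 names, puncture error and radial artery spasm, act before a patient can be enrolled. So does failure to cross the lesion with a wire from the arm. The technical success rate cannot register any of them, and the radial complication rate cannot register harm done during those attempts. A reader who has seen section 14 describe the endpoints as covering access could take the two rates as the results of trying the radial route. They describe patients in whom the route had already worked as far as the lesion.

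The second issue is safety capture. A consented patient who is punctured, possibly with a study sheath in place, and then fails eligibility has no protocol follow-up and falls outside the three sections that set the reporting window.

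**Working it through.** **Step 1: reproduce the plan's figures.** Inputs (Protocol 14.3 and 14.4; SAP 5 and 8.1): n = 129 limbs for efficacy and 129 subjects for safety; assumed rates 98% and 2%; goals 93% and 7%; one-sided 0.05; Clopper-Pearson bounds.

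- Efficacy lower bound for x successes: the 0.05 quantile of Beta(x, n − x + 1). 125/129 gives 0.9305 (pass); 124/129 gives 0.9202 (fail). Type I error P(X ≥ 125 | 129, 0.93) = 0.048. Power P(X ≥ 125 | 129, 0.98) = 0.882.
- Safety upper bound for e events: the 0.95 quantile of Beta(e + 1, n − e). 4/129 gives 0.0695 (pass); 5/129 gives 0.0798 (fail). Type I error P(E ≤ 4 | 129, 0.07) = 0.048. Power P(E ≤ 4 | 129, 0.02) = 0.882.

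The stated 88% reproduces for both endpoints.

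**Step 2: follow a consented patient through the rules**, reading enrollment as sections 11.1 and 13.1 define it.

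| Where the attempt ends | Enrolled? | In the primary endpoints? | Specific AE and deficiency window? |
|---|---|---|---|
| Radial access not gained | No (10.3) | No | No |
| Access gained, wire does not cross | No (7.1, criterion 10) | No | No |
| Wire crosses, another angiographic criterion fails | No | No | No |
| Enrolled, no device insertion attempted | Yes | No (14.1; SAP 6) | Yes |
| Stent system fails to track, deploy or withdraw, or femoral conversion | Yes | Yes, as a failure | Yes |

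Both rates are thus conditional on three things: access, transradial crossing and an attempted device insertion. The endpoint sections (Protocol 8.1; SAP 4), hypotheses (Protocol 14.2; SAP 8.4.1 and 8.5.1), sample-size text (Protocol 14.3; SAP 5) and population sections (Protocol 14.1; SAP 6) do not say that the rates are conditional in this way. The population sections give the insertion condition but not access or crossing. The SAP contains neither criterion 10 nor the definition of enrollment.

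**Step 3: passages that do not fit together.**

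- Section 10.3 asks that the patient has been assessed against the criteria; 11.1 and 13.1 ask that the patient is confirmed to qualify. On section 10.3 alone, a patient with failed crossing could be called enrolled.
- Section 10.2.2 says screen failures are not treated with study devices. In 11.1 step 3 the wire goes through the guiding sheath or a guide catheter, and the note at the end of 11.1 requires the study sheath as guiding sheath, so a study sheath may be in place before crossing is known. Exclusion 25 is judged after balloon angioplasty, for which 11.1 requires the study balloon.

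**Step 4: direction.** Let s be the success rate in the enrolled set and f the unknown share of attempts that fail access or crossing. Counting those as failures gives s(1 − f), which cannot exceed s. For safety, with complication rates c in enrolled and d in excluded patients, the all-attempts rate is c(1 − f) + d·f. This can move either way, depending on d.

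**Step 5: scale, with hypothetical counts.** In a supportive table, 126/129 (lower bound 0.941) becomes 126/130 (0.931) with one uncounted failure and 126/131 (0.921) with two. Four events in 129 (upper bound 0.0695) become 5/130 (0.079) with one more event in one more patient. The primary result does not change in any of these cases.

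**The case against.** The strongest reply is that this is a legitimate estimand. Sections 8.1.2 and 8.4 aim at the delivery system, and the guidewire is not a study device. Every condition is written in the Protocol, so a careful reader can derive the restriction. Later tracking, deployment, withdrawal and conversion failures all count. This stands, and it is why ITT should stay primary. It does not supply the missing statement where the rates are defined, or in the SAP.

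A reader might infer that event capture is simply ambiguous, because the opening of section 13, 15.3 and 17.1 have wording without an enrollment limit. That goes too far. Those lines cover a general duty to report concerns, source documents and product accountability, while 11.1, 13.1 and 13.6 clearly name enrolled subjects. Sections 13.3 and 13.7 to 13.9 also give routes for serious events and for CE-marked devices, including the sheath, with no stated enrollment limit. What remains is mainly non-capture of non-serious or purely puncture-related events.

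Screen-failure accounting also exists in part. Section 10.2.2 requires a documented reason and a log, and SAP 8.2 tabulates accountability. Neither asks for a split by puncture, access and crossing.

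**Conclusion.** The point holds as a cheap improvement. Both primary rates describe patients who had successful radial access, successful transradial crossing and an attempted device insertion. Followed as written, the plan leaves radial complications in punctured screen failures out of the safety result.

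Three stronger readings are not supported.

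- That the primary tests are invalid: for the enrolled set, size (0.048) and power (0.882) are as planned.
- That a bias can be computed: no rate of failed crossing is given. The risk-list category for access failure (below 0.002%, sections 5.1.2 and 13.2) is stated for use of the stent system, so it is not a puncture-failure rate. The 93.2% success in 5.4.1 and the 49 of 50 in 1.3 do not say whether failed access or crossing was counted.
- That the 93% and 7% goals rest on all-attempt denominators, so that the comparison is mismatched: the documents do not describe the denominators behind either goal.

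The conclusion assumes that enrollment is read as in 11.1 and 13.1. On the looser wording of 10.3 the boundary is unclear, which is a further reason to settle it.

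**What to change.** 1. State in Protocol 10.2.2, 11.1, 13.1 and 13.6 that, for every consented patient with an attempted radial puncture, adverse events are recorded from puncture to discharge and device deficiencies from first use or handling of a study device.
2. Keep ITT primary. Add to the SAP one supportive table of both primary endpoints for all radial attempts after each site's roll-ins, per limb for efficacy and per subject for safety. Count failed access as failure and show failed crossing both ways. State in advance how patients excluded for lesion anatomy alone are handled.
3. Tabulate post-puncture screen failures by reason under SAP 8.2.
4. Word the primary conclusion as conditional on radial access, transradial crossing and attempted device insertion.
5. Reconcile 10.2.2 with 11.1 and exclusion 25 on study-device use before eligibility is settled, and reconcile 10.3 with 11.1 and 13.1 on when a patient is enrolled.

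Cost: sample size, hypotheses and success rule do not change. Items 3 and 4 cost almost nothing. Items 1 and 5 need a protocol amendment with competent-authority and ethics approval (section 15.5.1), and item 1 needs a puncture flag and a short event form in the CRF. The supportive rates may look less favourable. Enrollment began in Q2 2022, so data on punctured patients screened before the amendment will be incomplete, and the table should say so.

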7.2 Exclusion Criteria

Subjects will be excluded if they meet ANY of the following exclusion criteria:

1. The patient has had/experienced any prior intervention/treatment to the target vessel within 90 days prior to enrollment (e.g., previously implanted graft in the aorta or target vessel; stroke; cryoplasty, laser or atherectomy; abdominal aortic aneurysm or aneurysm of the iliac, superficial femoral or popliteal artery).
2. Previously deployed stent at the site of the target lesion.
3. The patient has post-surgical stenosis and anastomotic suture treatments of the target vessel.
4. Requires general anesthesia for percutaneous transluminal angioplasty (PTA) and/or the stenting procedure.
5. Use of mechanical devices on or thrombolysis of the target vessel within 72 hours prior to the index procedure without complete resolution of the thrombus.
6. The patient is receiving any form of dialysis.
7. The patient is receiving any form of immunosuppressant therapy.
8. Planned amputation.
9. Established vasospastic disease.
10. Glomerular filtration rate (GFR) $<$ 30 mL/min within 7 days prior to the index procedure.
11. The patient has a history of neutropenia, coagulopathy, and/or thrombocytopenia.
12. Thrombophlebitis, uremia, or deep venous thrombus, within past 30 days prior to the index procedure
13. Bleeding diathesis.
14. Known allergies or intolerance to antiplatelet, anticoagulant or thrombolytic medications including but not limited to aspirin, clopidogrel bisulfate (Plavix®), ticlopidine (Ticlid®) or heparin that cannot be medically managed.
15. Known allergy or intolerance to Nitinol (nickel titanium).

RADIANT / P21-7701

Version: 7.0 / March 21, 2023

16. Known allergy to contrast agent that cannot be medically managed before treatment with steroids and/or antihistamines.
17. Known or suspected active infection at the time of the index procedure.
18. Patient is currently participating in another investigational drug or medical device study that has not completed primary endpoint(s) evaluation or clinically interferes with the endpoints from this study or is planning to participate in such a study prior to their completion of this study.
19. Patient has had a major surgical or interventional procedure unrelated to this study within 30 days prior to enrollment or is anticipated/planned to have such a procedure within 30 days after enrollment.

Exclusion criteria 20 through 25 would be assessed via baseline angiography performed at the time of index procedure:

20. Significant vessel tortuosity or other parameters prohibiting access to the lesion or 90° tortuosity which would prevent delivery of the stent device.
21. Noted perforation of the target vessel.
22. Stent placement required across or within 0.5 cm of the SFA/profundus femoris artery (PFA) bifurcation.
23. Cases of chronic total occlusion/in-stent restenosis/severe calcification in which there is pre-determined inability to treat the target lesion with a single stent, or procedures pre-determined to require stent-in-stent placement to obtain patency.
24. Presence of thrombus prior to crossing the lesion.
25. Successful PTA treatment of a target lesion in the SFA/PPA (defined as ≤ 50% stenosis after PTA treatment).

This study is designed to exclude children, pregnant women, and immunocompromised subjects, due to the nature of the procedure, device and indications.

8 Study Endpoints

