	
9. Established vasospastic disease10. Glomerular filtration rate (GFR) < 30 mL/min within 7 days prior to the index procedure11. The patient has a history of neutropenia, coagulopathy, and/or thrombocytopenia.12. Thrombophlebitis, uremia, or deep venous thrombus, within past 30 days prior to the index procedure13. Bleeding diathesis14. Known allergies or intolerance to antiplatelet, anticoagulant or thrombolytic medications including but not limited to aspirin, clopidogrel bisulfate (Plavix®), ticlopidine (Ticlid®) or heparin that cannot be medically managed.15. Known allergy or intolerance to Nitinol (nickel titanium)16. Known allergy to contrast agent that cannot be medically managed before treatment with steroids and/or antihistamines.17. Known or suspected active infection at the time of the index procedure.18. Patient is currently participating in another investigational drug or medical device study that has not completed primary endpoint(s) evaluation or clinically interferes with the endpoints from this study or is planning to participate in such a study prior to their completion of this study.19. Patient has had a major surgical or interventional procedure unrelated to this study within 30 days prior to enrollment or is anticipated/planned to have such a procedure within 30 days after enrollment.
--	--

Exclusion criteria 20 through 25 would be assessed via baseline angiography performed at the time of index procedure:

20. Significant vessel tortuosity or other parameters prohibiting access to the lesion or 90° tortuosity which would prevent delivery of the stent device
21. Noted perforation of the target vessel
22. Stent placement required across or within 0.5 cm of the SFA/profunda femoris artery (PFA) bifurcation
23. Cases of chronic total occlusion/in-stent restenosis/severe calcification in which there is pre-determined inability to treat the target lesion with a single stent, or procedures pre-determined to require stent-in-stent placement to obtain patency
24. Presence of thrombus prior to crossing the lesion
25. Successful PTA treatment of a target lesion in the SFA/PPA (defined as < 50% stenosis after PTA treatment)

RADIANT / P21-7701

Version: 7.0 / March 21, 2023

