- c. Select an appropriate size PTA balloon catheter, dilate the lesion with conventional technique and remove the PTA balloon from the patient.

7. Post Stent Placement

- a. Remove the guidewire and sheath from the body.
- b. Close entry wound as appropriate.

NOTE: It is required to use S.M.A.R.T. RADIANT as the stent delivery system, BRITE TIP RADIANT as the guiding sheath and SABERX RADIANT as the PTA balloon catheter (if pre-dilation and/or post-dilatation is performed) during the index procedure to be able to adequately evaluate the performance of all three (3) devices.

Though subjects are considered enrolled only from the time they are confirmed to qualify for study participation according to the eligibility criteria (i.e., upon completion of angiography), all events for enrolled subjects, which include all adverse events and device deficiencies, will be reported retroactive to when vascular access was established in the radial artery (i.e., time of puncture), in the case of adverse events, or initial use or handling of a study device, in the case of device deficiencies.

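### Exclusion 25 can be judged only after the study balloon has been used, and the documents do not consistently say how a patient who meets it is classified, followed or counted

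*Protocol*

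**What the plan says.** Protocol section 7.2 introduces the last group of exclusions with "Exclusion criteria 20 through 25 would be assessed via baseline angiography performed at the time of index procedure". Criterion 25, the last of them, is "Successful PTA treatment of a target lesion in the SFA/PPA (defined as ≤ 50% stenosis after PTA treatment". The synopsis words it as "Successful PTA treatment of a target lesion in the SFA/PPA (defined as < 50% stenosis after PTA treatment", so the two texts differ at exactly 50%.

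Section 11.1 requires BRITE TIP RADIANT as the guiding sheath and "SABERX RADIANT as the PTA balloon catheter (if pre-dilation and/or post-dilatation is performed) during the index procedure". Section 1.2 counts both among the study devices. Section 11.1 also places a separate arteriographic image after the dilatation.

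On status, section 10.3 treats a patient as enrolled only once every eligibility criterion has been assessed. Sections 11.1 and 13.1 describe subjects as enrolled from when they are "confirmed to qualify for study participation according to the eligibility criteria (i.e., upon completion of angiography". Under section 10.2.2, a consented patient found not to qualify "will be considered a screen failure and will neither be treated with the study devices nor followed per protocol". Section 11.3 records failure to implant as a treatment failure and follows an enrolled patient without a stent for safety to 30 days.

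The ITT set (Protocol section 14.1; SAP section 6) takes enrolled subjects in whom insertion of a device was attempted. It does not name the device.

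**The concern.** Take an SFA patient who meets every criterion on the baseline angiogram, is pre-dilated with SABERX RADIANT, and has residual stenosis low enough to meet criterion 25. Radial access, wire crossing and study-device use have all taken place. The documents give no single answer on whether this patient is enrolled, is followed, has adverse events reported, or enters the primary analyses. The SAP has no rule for the case.

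Two things are at stake. First, a patient exposed to the study sheath and balloon through the radial artery can drop out of the safety data of a trial whose primary safety endpoint is radial access complications. Second, sites report enrolment status after the index procedure (section 11.4), so the classification can be made with the balloon result known. In a single-arm trial judged against fixed goals, that choice should not be open.

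**Working it through.** **Step 1: what criterion 25 refers to.** It could mean angioplasty before the index procedure. But inclusion 11b already requires at least "50% stenosis in the SFA and/or PPA". A lesion below 50% at baseline angiography fails 11b, so on that reading criterion 25 adds nothing except at exactly 50%. Its working meaning is therefore angioplasty during the index procedure, which must use study devices.

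**Step 2: the three possible classifications.**

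| Reading | Support | Follow-up and event reporting | Technical success analysis |
|---|---|---|---|
| A. Screen failure | 10.3 (all criteria assessed first); 10.2.1 (verification before implantation); 11.4 (status reported after the procedure) | No follow-up (10.2.2); reporting in 11.1, 13.1 and 13.6 is for enrolled subjects | Not counted |
| B. Enrolled, ITT device means any study device | Angiography parenthetical in 11.1 and 13.1 | Safety follow-up to 30 days (11.3) | Counted as a failure |
| C. Enrolled, ITT device means the stent system only | Same parenthetical; 8.1.2 and 11.3 use the term study device for the stent | As B | Outside ITT |

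Under A, the section 10.2.2 statement that screen failures are not treated with study devices is untrue for this patient.

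**Step 3: reproduce the stated power.** Inputs from Protocol section 14.3 and SAP section 5: n = 129 limbs, assumed success 98%, goal 93%, one-sided exact 95% Clopper-Pearson bound. With f failures the lower bound is the 5% quantile of Beta(129 − f, f + 1).

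- f = 4: 93.05%, pass.
- f = 5: 92.02%, fail.

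Power = P(X ≤ 4) with X ~ Binomial(129, 0.02) = 0.882. This matches the stated 88%.

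**Step 4: effect under each reading.** Let k be the number of criterion-25 limbs. The documents do not give k; the values below are assumptions.

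Reading B, with the k limbs inside the 129: chance of passing = P(X ≤ 4 − k), X ~ Binomial(129 − k, 0.02).

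| k | Chance of meeting the goal |
|---|---|
| 0 | 0.882 |
| 1 | 0.746 |
| 2 | 0.532 |
| 3 | 0.280 |

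Reading A: if enrolment continues to 129 limbs, the chance stays at 0.882.

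Reading C: no limb becomes a failure. If the lost limb is not made up, however, 128 limbs allow only 3 failures and the chance is P(X ≤ 3), X ~ Binomial(128, 0.02) = 0.746.

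**Step 5: plausible k.** Assume the minimum of 30 subjects per indication applies within the 129, with one indication per subject. Femoropopliteal subjects then number 30 to 129 − 30 = 99. If 1% to 3% of them met criterion 25, k would run from 0.01 × 30 = 0.3 to 0.03 × 99 = 2.97, or about 0.3 to 3 patients. Pre-dilation is optional (section 11.1), and a directly stented lesion is never tested against criterion 25.

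**The case against.** A reader might infer that a good angioplasty is bound to be scored as a failure of the stent system, with the power loss tabulated above. The documents do not support that. Section 10.3 requires all criteria to be assessed before enrolment. Section 10.2.1 requires eligibility to be verified before implantation, not before ballooning. Completion of angiography could include the post-dilatation image. Even for an enrolled patient, the ITT wording must be read to include the sheath or balloon. The 0.75, 0.53 and 0.28 figures need both conditions.

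A reader might also infer that SABERX RADIANT would be assessed only where pre-dilation went badly. That does not fit the endpoint, which is scored on device handling and on final residual stenosis below 30% at the end of the procedure (sections 8.2 and 14.4.2). A balloon-only result of 30% to 49% would meet criterion 25 yet fail the SABERX definition. There is selection on residual stenosis, but its direction is unknown.

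The threshold mismatch affects only a reading of exactly 50%. The vigilance duties in section 13.9 would still send serious incidents with the CE marked devices to the authorities.

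These points narrow the concern but do not remove it. The better-supported reading is the one that leaves a device-exposed patient without study follow-up, and vigilance reporting does not restore that patient to the study's safety data.

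**Conclusion.** The conflict is real and should be corrected. It is a classification gap; the sample size calculation is correct on its own inputs.

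The firm part is safety. On the better-supported reading, patients with radial access and study-device use leave the primary safety denominator, the 30-day follow-up and the SABERX data. This holds whatever their number.

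The effect on technical success is conditional. There is none under the screen-failure reading, provided enrolment continues to 129. It is material only if such patients are enrolled and sheath or balloon insertion counts for ITT, because the rule tolerates only 4 failures. The frequency is unknown; about 0.3 to 3 patients is an illustration resting on an assumed 1% to 3%. How these patients should count for technical success is a design choice for the sponsor, since the documents do not settle it.

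**What to change.** 1. Move criterion 25 out of the baseline-angiography list. Reconcile sections 7.2, 10.3, 11.1 and 13.1 so that the time of enrolment relative to pre-dilation is fixed in advance.
2. State in Protocol section 14.1 and SAP section 6 which device defines ITT. Prespecify one classification, for technical success, of a patient with successful angioplasty and no stent attempt.
3. Amend section 10.2.2 and the reporting scope in sections 11.1, 13.1 and 13.6. Any patient in whom the study sheath or SABERX RADIANT was inserted is then followed for safety to 30 days, has events and deficiencies reported, and enters a supportive access-site safety analysis. Any SABERX use in that patient enters the SABERX results.
4. Reconcile the synopsis and section 7.2 on the residual-stenosis threshold. This review does not say which is right.

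The post-dilation reading will still be made at the site with the balloon result in view. What the change removes is the freedom to decide afterwards what that reading means for enrolment, follow-up and analysis. The cost is Protocol and SAP wording, a few extra patients followed to 30 days, and one supportive analysis.
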